Previously, we have examined the relationship between trauma and adverse outcomes but have not specifically focused on older patients ²⁰⁻²². It is possible that the immune systems of older patients react differently to injury when compared to younger cohorts, and this may increase vulnerability to MODS ^{14,23,24}. Decreased skeletal muscle mass in older people is reported to impair immune system function in intensive care patients²⁵ and severe injury may further alter immune cell activity, causing physiological changes leading to adverse outcomes^{26,27}. Altered metabolism after trauma is associated with increased inflammatory responses²⁸ and together with the nutritional deficits observed in critically injured older people²⁹ these may contribute to age-related MODS. Frailty is also known to reduce physiological function ^{30,31} and frailty in older people independently predicts in-hospital complications such as pneumonia or deep vein thrombosis after injury ³². Therefore it may be that frailty rather than age increases the risk of MODS after severe injury. Previous trauma studies suggest that both older age and frailty are associated with decreased longer-term independence after injury ^{32,33}. However the impact of MODS on longer-term function, dependence and recovery in older people has not been investigated. The lack of UK-based evidence means that the prevalence, predictors and outcomes of MODS in our older trauma patients are unknown.

This prospective observational study will evaluate the patterns of MODS in trauma patients and determine to what extent it is related to ageing and frailty. By understanding specific age-related predictors or drivers of MODS we aim to identify treatment or prevention strategies which will enhance recovery for severely injured older people. MODS is also associated with late, indolent death, and by studying patterns of this mortality in older patients we may be able to prognosticate futility. This may enable stratification of older patients most likely to respond to intervention and those who would benefit from supportive or palliative care. Finally, evidence of how MODS impacts longer-term recovery and quality of life will support rehabilitation practice, and where appropriate, self-managed recovery for older trauma patients and their support networks.

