6. METHODOLOGY

Study Design

This is a pan-London prospective observational study which aims to characterise organ dysfunction in older trauma patients \geq 65 years. All adults admitted to an adult critical care unit within one the London Major Trauma Centres (MTCs) will be considered for enrolment, with younger patients (<65 years) recruited as a control group.

Settings

There are four MTCs in London. Each site will have a nominated Principal Investigator (PI). Organ injury scoring training will be provided for local research nurses or data collectors prior to study commencement. Two funded research nurses from Queen Mary University of London (QMUL) will support patient enrolment, data collection and data quality monitoring across the four MTCs. Each site will be supported by an on-line information folder with the protocol, guidance/explanatory notes and contact details of the Principal Investigator. For this study, a critical care unit is defined as either an Intensive Care Unit (Level 3 care) or a combined unit of Intensive Care (Level 3 care) and High Dependency Unit (Level 2 care).

Inclusion Criteria

- Adult major trauma patients (≥16 years of age) admitted to adult critical care within one of the four London Trauma System MTCs. This includes direct admissions from the Emergency Department, admissions from the operating theatre or from a ward, transfers from other facilities and readmission to critical care.

Exclusion Criteria

- Patients with a burns-only injury
- Patients who are prisoners
- Patients who decline to provide informed consent or do not have consultee consent

Study Design / Plan – Study Visits

Trauma patients (≥16 years of age) admitted to MTC critical care during the enrolment phase of the study (two years in total) will be identified by the local PI together with clinical care staff. The local PI will be responsible for ensuring patient enrolment, participant consent, data collection, patient detail de-identification, data entry and storage. Data from routine clinical care records will be recorded daily by local and QMUL research nurses whilst the patient is admitted to the critical care unit.

The clinical data collection will include:

- Demographics: Age within a range, gender, co-morbid disease, pre-injury medication
- Injury variables: Mechanism of injury, Injury Severity Score (ISS)
- Organ dysfunction: The frequency, pattern and severity will be measured daily using Sequential Organ Failure Assessment (SOFA) scoring

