- Total number of days on organ support (CTCOFR score)
- Immune cell function: Daily clinical measures of lymphocyte and neutrophil counts
- Adverse events: Such as infection, delirium, stroke or cardiac dysfunction
- Nutrition: Nutritional requirements, nutrition intake and weight measurements
- Frailty screening using the Edmonton Frail Scale (https://www.nscphealth.co.uk/edmontonscale-pdf)
- Length of stay: In critical care and total hospital stay
- Mortality: Mode and timing

[figure not shown]
As soon as clinically appropriate (determined by the clinical care team in charge of the patient), consent will be sought for inclusion of data into the study and long term follow up. If the patient remains incapacitated due to injury or treatment, consent will be sought from a personal or nominated consultee.

At 12 months post injury patients will be approached by letter, email or telephone (according to patient wishes) and health-related quality of life and longer-term recovery data will be collected using the EuroQol-5D (EQ5D) questionnaire. This was chosen as it has been previously validated to capture outcomes in trauma patients including older people and takes approximately 15 minutes to complete.

Study Scheme Diagram

Each MTC will be identified by a number rather than name.

Eligible trauma patients admitted to the critical care unit during the study period will be identified by the clinical care team.

The PI and research nurses have responsibility to ensure patient anonymity is protected and maintained. They will also ensure that patient identities are protected from any unauthorised parties. Information regarding study patients will be kept confidential and managed in accordance with the Data Protection Act, NHS Caldicott Guardian, The Research Governance Framework for Health and Social Care and Research Ethics Committee Approval.

Although patient identifiable data will be available to research staff they will not be entering it on to the paper case record form (CRF). The de-identified data required for this study is already recorded as part of routine clinical care and as part of the Intensive Care National Audit and Research Centre (ICNARC) audit. Organ failure scoring is not usually conducted as part of routine clinical care however it uses parameters that are recorded by critical care clinical staff on a daily basis.

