Paper CRFs will be stored within a locked office in each centre (only accessible to the centre PI and data collectors) and then entered onto the password protected study website by QMUL research nurses.

A password protected coding log which will include identifiable patient data (name, address and date of birth) for patients who have consented to long term outcome follow-up. This will be transferred to [name] (CI) at the end of the in-hospital data collection period. At ten months after injury the NHS Health and Social Care Information Centre (NHS Spine) or patients General Practitioner (GP) will be contacted to ensure that the patient is still alive at this time point. This will avoid erroneous long term follow up and exposing relatives to undue distress. At 12 months post injury, the EQ5D and questionnaire will be administered to each participant who has provided informed consent.

	In critical care	At discharge from hospital	10 month post injury NHS spine check/GP check	12 months post injury
Enrolment	х			
CRF initiation	х			
Informed	х			
consent				
Daily SOFA score	х			
and outcomes				
recorded				
CRF completion		х		
Long term			х	х
follow up				

Schedule of Assessment

End of Study Definition

The study will be formally completed when 12 month follow up for all patients has been obtained and data analysis is complete.

Sample size:

We are planning a study of older patients (≥65 years) and younger (<65 years) controls. Prior research data suggest that the MODS rate among younger patients is 23% and for older patients is 33%. If the true MODS rate in older people is 0.33, we will need to include 259 older subjects and 414 younger subjects per year to be able to reject the null hypothesis that the prevalence of MODS for older and younger patients is equal (power 0.80, alpha 0.05). The total sample size for the two year period is 1346 (518 older patients and 828 younger controls). Each London MTC will aim to enroll:

130 older patients (>64 years) and 207 younger patients (<65 years).

Methods of analysis:

Statistical analysis will be performed using SPSS v.23 (IBM Corporation, Armonk, NY,USA). A p value of <0.05 is considered statistically significant for univariate analysis. De-identified data will be cleaned and categorical data formatted into binary fields for analysis. Normal distribution will be assessed with the Shapiro-Wilk test.

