Univariate analysis of variables between the two age groups (< 65 years and ≥65 years) will be conducted using unpaired students t-tests or Mann Whitney U tests (for parametric and non-parametric data respectively). Analysis of more than two groups (for example thresholds of immune counts or degrees of organ dysfunction) will be conducted using ANOVA or Kruskal Wallis tests. Chi-squared statistic or Fisher's exact tests will be used to compare proportions of MODS between the two cohorts.

Multivariable regression analysis will be used to determine statistically independent relationships between MODS and age plus other significant independent variables (such as the effect of injury severity, blood transfusion, on the development of MODS). Multivariate linear regression will be used to analyse continuous dependent variables and binary logistic regression for binary dependent variables. Results of linear regression will be reported as Beta co-efficient with 95% confidence intervals, and for logistic regression adjusted Odds ratios (OR) with 95% confidence intervals.

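### Age, the exposure of interest and main confounder of frailty, is collected only in bands of unstated width, so the data set may not support a continuous age term in the age-versus-frailty analysis

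*Protocol*

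**What the plan says.** The Introduction (section 4) states that the study will "determine to what extent it is related to ageing and frailty", and gives the working hypothesis: "Therefore it may be that frailty rather than age increases the risk of MODS after severe injury". Age and frailty are therefore to be separated.

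The list of clinical data in section 6 (Study Design / Plan – Study Visits) has age as a banded item: "Demographics: Age within a range, gender, co-morbid disease, pre-injury medication". Neither the width of the bands nor their cut-points are given. Frailty is collected by a named instrument: "Frailty screening using the Edmonton Frail Scale".

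Date of birth appears in one place, a password-protected coding log holding "identifiable patient data (name, address and date of birth) for patients who have consented to long term outcome follow-up". Section 6 also says that identifiable data are kept off the paper CRF, and section 9 that patients who die in hospital are included with de-identified data.

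Under Methods of analysis, three statements bear on how age is used:

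- "De-identified data will be cleaned and categorical data formatted into binary fields for analysis"
- "Univariate analysis of variables between the two age groups (< 65 years and ≥65 years", for the two-group comparisons
- "Multivariable regression analysis will be used to determine statistically independent relationships between MODS and age plus other significant independent variables", with no form given for age and no mention of frailty

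**The concern.** Frailty can be expected to rise with age, within the older group as well as across the whole cohort. If the age term in the model is coarse, the age differences left inside each category are partly picked up by frailty. The error then favours the study's own hypothesis, that frailty rather than age matters.

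The choice of age term can wait for a statistical analysis plan. What is recorded cannot: a later plan can choose among codings of the bands but cannot turn them back into years. Recovery from the coding log would be incomplete, because patients without follow-up consent are not in it. That notably includes in-hospital deaths without such consent, so the gap would be related to outcome.

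The sentence on binary fields adds to the doubt. Banded age is categorical, so the sentence could be taken to cover it.

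**Working it through.** **1. The plan's own figure.** Inputs from Sample size (section 6): MODS 33% in older and 23% in younger patients, power 0.80, alpha 0.05, 259 older and 414 younger per year (ratio r about 1.6). Two-sided, without continuity correction:

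n(older) = [1.96·√((1 + 1/r)·p̄(1 − p̄)) + 0.8416·√(p₁q₁ + p₂q₂/r)]² / (p₁ − p₂)²

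p̄ = (0.33 + 1.6 × 0.23)/2.6 = 0.2685

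n(older) = (1.107 + 0.485)² / 0.10² = 253.4, so 254 older and 407 younger.

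This is within 3% of the stated 259 and 414. Power is 80.8% at 259/414 and 97.9% at 518/828. The calculation uses only which side of 65 a patient falls on, so banding does not alter it if the bands break at 65.

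**2. Information kept by each coding.** Assumption, not in the protocol: ages uniform on 16-65 and on 65-95, mixed 828:518 (weights 0.615 and 0.385). The share of information kept is the between-category share of the variance of age.

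- Within groups: 0.615 × 49²/12 + 0.385 × 30²/12 = 151.9
- Between groups: 0.615 × 0.385 × (80 − 40.5)² = 369.4
- Split at 65 only: 369.4 / (369.4 + 151.9) = 0.71
- Four bands (cuts at 45, 65, 80): 0.92
- 10-year bands breaking at 65: 0.98

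**3. Effect on the frailty result.** Simulated studies of 518 older and 828 younger patients. The log-odds of MODS are linear in age and calibrated to 23% and 33%. Frailty is correlated with age but has no effect of its own (true OR 1.00). In the first two rows younger ages are uniform and older ages are 65 plus an exponential tail (mean 10 years, capped at 35); the odds ratio for age is about 1.16 per decade. The third and fourth rows use uniform ages within groups.

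Frailty declared significant at nominal 5%:

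| Age-frailty correlation | Studies | Age in years | 10-year bands | Four bands | Split at 65 |
|---|---|---|---|---|---|
| 0.26 | 500 | 4.4% | 4.4% | 4.6% | 7.4% |
| 0.43 | 500 | 5.8% | 5.8% | 5.6% | 11.2% |
| 0.50 | 1,500 | 4.7% | 4.7% | – | 10.9% |
| 0.53 | 600 | 4.8% | – | – | 8.5% |

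In the third row, three bands (cuts at 45 and 65) gave 6.3%. One further simulation gave 6.3% with age in years, 6.5% with 10-year bands and 12.0% with the split at 65. With 500 studies the simulation error is about √(0.05 × 0.95/500) = 1 percentage point.

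The excess of the 65-year split over age in years is therefore 3.0 points (7.4 − 4.4) to 6.2 points (10.9 − 4.7).

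Large-sample odds ratios for frailty under the first two settings: 1.01 with age in years, 1.01 to 1.02 with 10-year bands, 1.03 to 1.04 with four bands, and 1.08 to 1.13 with the split at 65.

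**The case against.** The strongest case on the other side is that the protocol never says age will be dichotomised in the adjusted model. The sentence on binary fields does not mention age, and it may mean ordinary 0/1 indicator coding, which loses nothing. The two-group wording concerns univariate comparisons. The same section plans analyses of more than two groups, so ordered variables are not all reduced to two levels. With bands of ordinary width, the harm is close to nil. The shape of the age term and the coding of frailty can properly be left to a statistical analysis plan. All of this stands.

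It also rules out several stronger conclusions that a reader might infer:

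- **That every age from 65 to 95 becomes one value.** This joins two sentences that the protocol does not join.
- **That a dose-response with age cannot be estimated.** Three or more ordered bands allow a trend or band-by-band estimates.
- **That 1346 patients are worth only about 950.** The product 0.708 × 1346 = 953 describes a linear age effect under the worst coding. The sample size was set for a two-group comparison that loses nothing.
- **That a band might straddle 65.** The 65-year split governs design, enrolment targets and analysis, and nothing suggests a band crossing it.
- **That the loss is permanent.** Research staff can see identifiable data, the data come from routine records, and date of birth is logged for some patients. The documents do not show that age is irrecoverable, only that it is not planned as analysis data.

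What the objection does not answer is that the collection rule is stated here, for the study's central variable, without the detail that decides whether it is harmless.

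**Conclusion.** The point holds as a cheap improvement to what is recorded. Age is both the exposure and the main confounder of frailty, and the protocol plans to hold it in bands of unspecified width. Exact age is not a listed analysis variable, and the log of follow-up consenters cannot supply it for everyone.

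The consequence runs from negligible (10-year bands breaking at 65) to material (age cut only at 65, with frailty falsely significant in roughly 7-12% of studies against about 5%). The protocol does not tell the reader where in that range the study lies.

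These sizes rest on assumed age distributions, assumed age-frailty correlations of 0.26 to 0.53 and a linear age effect. A steeper or non-linear effect would enlarge the bias. The primary chi-squared comparison and the sample size are untouched, provided that the bands break at 65.

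**What to change.** - **Data collection list, section 6:** record age in completed years on the CRF for every patient, top-coded (for example at 90 and over) if de-identification requires it. Whole years need no date of birth, so the rule against identifiers on the CRF is respected.
- **Methods of analysis:** keep the 65-year split for the headline comparison, and state that age enters the adjusted MODS models as a continuous term beside frailty. Its functional form can be left to the statistical analysis plan.
- **Binary fields:** reword the sentence to say that categorical variables are coded as 0/1 indicators, so that it cannot be read as dichotomising age.

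The cost is one CRF field and a sentence or two of analysis text. The downside is slightly more identifying data, which top-coding limits. If age in years cannot be held, the fallback is to state narrow bands with a break at 65.

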4. INTRODUCTION

For the first time there are 11 million people aged 65 or over in the UK¹. The number of older people suffering traumatic injury is increasing ²⁻⁶. In those who survive the initial period after injury a significant proportion goes onto develop adverse events such as multiple organ dysfunction (MODS) ^{7,8}. This occurs as a result of an exaggerated systemic inflammatory response following major tissue trauma⁹, where one or more organs do not function as they did prior to the traumatic injury. Recent reports suggest that MODS affects up to 33% of trauma patients ^{7,10-12}. Younger injured people who develop MODS usually recover quickly¹³, whereas older patients appear to suffer prolonged organ dysfunction, which is complicated by persistent immunosuppression and infectious episodes^{10,14,15}. This extends hospital stay, increases resource use and delays recovery after trauma ^{11,12}. MODS in older people is also associated with increased mortality ¹⁶⁻¹⁸ characterised by late, indolent death ^{14,19}. International evidence suggests that older age is strongly associated with MODS after trauma ^{7,11,12,14}, however the age-related characteristics that contribute to this burden in the UK have not been reported.

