5. STUDY OBJECTIVES

This study aims to:

- Identify the prevalence, severity and patterns of MODS in older patients
- Determine predictors and risk factors of developing MODS for older patients
- Identify age related characteristics that contribute to MODS
- Examine the mode of mortality associated with MODS
- Analyse the relationship between MODS and longer-term recovery and quality of life for older patients

The primary outcome is the presence of MODS during the critical care admission period. An individual Sequential Organ Failure Assessment (SOFA) score of 1 in any organ represents dysfunction. Multiple organ dysfunction syndrome (MODS) is defined as a total daily SOFA score of >5.

Secondary outcomes are in-hospital mortality, ventilator use, level of organ support, adverse events such as infection or stroke, critical care stay and total length of stay. Longer terms outcomes are quality of life and recovery at one year post injury.

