9. ETHICS

This study will be carried out in accordance with the ethical Principals in the Research Governance Framework for Health and Social Care, Second Edition, 2005 and its subsequent amendments as applicable and applicable legal and regulatory requirements. The study has been reviewed and approved by the London South East Research Ethics Committee on 26th October 2016.

Each participant in the study will be approach for informed consent to allow non-clinical care staff (QMUL research nurses and Chief Investigator) to:

- 1. access the status of the participant at ten months post injury via NHS Health and Social Care Information Centre or the patients GP
- 2. follow up the participant via telephone, letter or email at 12 months post injury

Incapacity:

For most of the severely injured patients admitted to a critical care unit, there will be a period of time where they require sedation and ventilation (life support) resulting in temporary incapacity. Specific injury factors such as hypoxia, haemorrhage or the presence of a traumatic brain injury may also add to the incapacity. During the in-hospital stage of the study, all of the data being collected is part of routine clinical care therefore there is time to wait to see if the patient regains capacity. Once this occurs, the study can be explained by the local collaborator and a participant information sheet given to the patient for 24-48 hours prior to seeking informed consent.

In those patients where capacity is not regained during the critical care stay every effort will be made to identify and consult with someone who knows the person who lacks capacity, such as a relative or significant other next-of-kin. The study will be explained to the personal consultee. This individual will be provided with a personal consultee written information sheet prior to seeking consent on a personal consultee consent form.

Where the person who lacks capacity has no family or friends who are willing and able to fulfil this role the local collaborator will ask the patients critical care consultant to provide consent as a nominated consultee.

Patients who die during the in-hospital study period will have their de-identified data included in the study.

10. DATA HANDLING AND RECORD KEEPING:

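### The only vital-status check is at ten months, two months before the 12-month EQ-5D contact, so it cannot fully do what the protocol says it will do

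*Protocol*

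**What the plan says.** Protocol section 6 (Methodology) sets two long-term follow-up steps.

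- **Ten months after injury.** NHS Spine or the GP "will be contacted to ensure that the patient is still alive at this time point". The reason given is: "This will avoid erroneous long term follow up and exposing relatives to undue distress".
- **Twelve months after injury.** "At 12 months post injury, the EQ5D and questionnaire will be administered to each participant who has provided informed consent". The same section says that contact is by letter, email or telephone, as the patient prefers.

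The Schedule of Assessment table shows the same two steps and no further status check. The consent items in section 9 (Ethics) match it. The first allows study staff to "access the status of the participant at ten months post injury via NHS Health and Social Care Information Centre or the patients GP"; the second covers the 12-month contact itself. No status look-up at 12 months is listed.

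On death as an outcome, section 5 (Study Objectives) begins its list: "Secondary outcomes are in-hospital mortality, ventilator use, level of organ support, adverse events such as infection or stroke, critical care stay". It names no mortality outcome after discharge, and section 6 has the case record form completed at hospital discharge. One objective is nevertheless long-term: "Analyse the relationship between MODS and longer-term recovery and quality of life for older patients".

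**The concern.** The protocol states flatly that the ten-month check will prevent two harms. A check shows only that the patient was alive when it was made. For the two months before contact it says nothing, so a letter, email or call may reach the household of someone who has died since.

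There is also a data consequence. If no reply comes, the study has no planned source that separates a death in months 10 to 12 from a living patient who did not answer. In this population the distinction matters: section 4 (Introduction) describes the mortality linked to MODS in older people as "characterised by late, indolent death", and the long-term objective concerns the same patients. An analysis plan cannot repair this, because it depends on when status is looked up, what is recorded, and what patients have consented to.

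**Working it through.** **Does the check cover the contact date?** Setting the sections side by side:

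| Item | Time after injury | Where |
|---|---|---|
| Status look-up | 10 months | Section 6 text; Schedule of Assessment; section 9, consent item 1 |
| EQ-5D contact | 12 months | Section 6 text; Schedule of Assessment; section 9, consent item 2 |
| Any look-up between 10 and 12 months | none stated | – |
| Date of death found at the look-up | recording not stated | – |

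The unprotected interval is 12 − 10 = 2 months. The three places agree with one another, so this is a consistent design choice and not a slip in one section.

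**How many patients could be affected?** The protocol gives no figure for this, so there is none to reproduce. The only input from the documents is the planned total: 2 × (259 + 414) = 1346. Two quantities have to be assumed:

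- *s*, the share of the 1346 who are alive, consenting and followed at ten months: 70% to 90%;
- *q*, the share of those who die in the following two months: 0.5% to 3%.

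Expected deaths missed by the check = 1346 × *s* × *q*.

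| *q* | *s* = 70% | *s* = 80% | *s* = 90% |
|---|---|---|---|
| 0.5% | 4.7 | 5.4 | 6.1 |
| 1% | 9.4 | 10.8 | 12.1 |
| 2% | 18.8 | 21.5 | 24.2 |
| 3% | 28.3 | 32.3 | 36.3 |

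The range is about 5 to 36 patients, or 0.3% (4.7/1346) to 2.7% (36.3/1346) of the planned total.

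**Effect on the response rate.** If every such death were counted as a non-response, the response rate among patients alive at 12 months would be understated by a factor of 1 − *q*, that is 0.97 to 0.995. The documents give nothing with which to split the missed deaths by MODS or by age group.

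**The case against.** The strongest reply is that this is a minor operational matter. The interval is short, few deaths are likely in it, and a telephone call or returned letter may itself reveal the death. The protocol has no rule that codes a late death as a non-response, and it does not say that relatives will be contacted. All of this stands, and it is why the consequences are worded here as possible and the number as probably small. It does not rescue the statement that the check will prevent these events. Learning of a death through the contact is what the check was meant to avoid.

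The reply can add that a later look-up is not free, because section 9 limits status access to ten months and ethics approval has already been given. That also stands, and the cost is counted in the fix.

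A reader might go further and infer that the association between MODS and quality of life will be estimated in survivors only and so be biased towards no difference. The documents do not support this, for four reasons.

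- The protocol states no survivors-only analysis. Linear regression is assigned to continuous outcomes in general and EQ-5D is not named. How deaths enter the analysis may be set out in an analysis plan that is not at hand.
- Deaths are not ignored. Patients who die in hospital stay in the data set, mode and timing of death are collected, and deaths found at ten months are known to the study.
- Section 4 wants the quality-of-life evidence to support rehabilitation and self-managed recovery, which is a legitimate question about survivors. Scoring death as zero answers a different question and is a debatable choice.
- Any size given to such a bias rests wholly on assumed inputs. With 12-month mortality of 20% v 10% and survivor EQ-5D of 0.60 v 0.70 (MODS v no MODS), the survivor difference is −0.10, and the difference with death scored zero is 0.80 × 0.60 − 0.90 × 0.70 = −0.15, so the survivor figure is two-thirds of it. With equal survivor scores it is none of it.

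The two matters are also separate: EQ-5D could come only from the living even if status were checked on the day of contact.

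**Conclusion.** The point holds as a limited defect of timing. The single check precedes the contact by two months, is not repeated, and so cannot fully secure the aim that section 6 claims for it. Patients who die in between may be approached and may be recorded no differently from non-responders.

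That the gap exists follows from the protocol text alone. Its size does not: about 5 to 36 patients of 1346 rests on the assumed 70–90% followed and 0.5–3% dying in the window. Section 4 does not say how late the late deaths occur, so it cannot narrow that range. The number is probably small. The change is worth making because it is inexpensive, protects bereaved families and separates death from non-response at 12 months. No conclusion is drawn about bias in the MODS and quality-of-life analysis.

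**What to change.** 1. Move the NHS Spine or GP check to immediately before the 12-month contact, or keep the ten-month check and repeat it then.
2. Record vital status and date of death to 12 months for every patient followed.
3. Amend the Schedule of Assessment table and the first consent item in section 9, which now names ten months only, so that the later look-up is covered.
4. Report deaths by 12 months beside the EQ-5D results, and describe those results as applying to survivors who responded.

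**Cost.** A protocol and consent amendment is needed, probably with ethics review, and patients who have already consented under the ten-month wording must be considered in it. Repeating the check adds a second look-up per patient; moving it does not. No change to the sample size or the EQ-5D instrument is needed. If the amendment cannot be made, the claim in section 6 should at least be softened to say that the check reduces misdirected contact and does not exclude it.

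### The sample giving 80% power (259 older + 414 younger = 673) is labelled an annual need and doubled to 1346, so the stated power of 0.80 is not the power of the planned study

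*Protocol*

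**What the plan says.** All the figures are in the protocol, section 6 (Methodology), under the sample size heading. The assumed rates are given as "Prior research data suggest that the MODS rate among younger patients is 23% and for older patients is 33" per cent. The error rates are "power 0.80, alpha 0.05", with no mention of one or two sides. The hypothesis to be rejected is that "the prevalence of MODS for older and younger patients is equal".

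The requirement is then put in annual terms: "we will need to include 259 older subjects and 414 younger subjects per year to be able to reject the null hypothesis". The next step multiplies by two: "The total sample size for the two year period is 1346 (518 older patients and 828 younger controls"). The synopsis (section 3) repeats 1346 as the number of participants, and each of the four centres is given a target of 130 older and 207 younger patients on the same basis.

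The analysis is a single comparison. Under methods of analysis the protocol says: "Chi-squared statistic or Fisher's exact tests will be used to compare proportions of MODS between the two cohorts". The synopsis describes the primary analysis in the same way.

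**The concern.** A power calculation for comparing two proportions returns the number of patients who enter the test. It has no time unit. An annual requirement would make sense only if each year's intake were tested separately at 80% power, and neither the synopsis nor section 6 plans this. If 259 and 414 are the complete requirement for the test, doubling them produces a study whose power is not 0.80.

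The sponsor, the funder and the sites rely on these figures. As written, 1346 reads as the minimum for 80% power to detect 33% against 23%. A study that recruited, say, 1000 patients would then appear underpowered for its primary outcome when it was not. The difference that the planned sample can actually detect is not stated anywhere.

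**Working it through.** **Inputs (protocol, section 6).** p1 = 0.33 (older), p2 = 0.23 (younger), difference 0.10, alpha 0.05, power 0.80, allocation ratio k = 414/259 = 1.598. Two-sided alpha is assumed, so z = 1.960 for alpha and 0.842 for power.

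**Step 1: reproduce the plan's figure.** The pooled rate is p̄ = (0.33 + 1.598 × 0.23)/2.598 = 0.2685.

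- Pooled variance under the null: n(older) = [1.960·√(p̄(1−p̄)(1+1/k)) + 0.842·√(p1(1−p1) + p2(1−p2)/k)]² / 0.10² = [1.960·√0.3193 + 0.842·√0.3319]² / 0.01 = 253.5. That is 254 older and 407 younger, 661 in all.
- Unpooled variance: n(older) = 0.3319 × (1.960 + 0.842)² / 0.01 = 260.5, with 416.4 younger, about 677 in all.
- Continuity-corrected: 270 + 432 = 702.
- One-sided, pooled: 201 + 322 = 523.

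The stated 259 lies between the pooled and unpooled results and is within 3% of both. No variant tried gives exactly 259. The one-sided calculation is far off, so two-sided is the reasonable reading. Hence 259 + 414 = 673 is the **total** for one test at 80% power.

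**Step 2: power at each sample size.** Power = Φ[(0.10 − 1.960·SE0)/SE1], where SE0 = √(p̄(1−p̄)(1/n1+1/n2)) and SE1 = √(p1(1−p1)/n1 + p2(1−p2)/n2).

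- 259/414: SE0 = 0.0351, SE1 = 0.0358; (0.10 − 0.0688)/0.0358 = 0.871; power 0.808.
- 518/828: SE0 = 0.0248, SE1 = 0.0253; (0.10 − 0.0487)/0.0253 = 2.028; power 0.979.

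The choice of test makes little difference:

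| Test | 259/414 | 518/828 |
|---|---|---|
| Chi-squared | 0.808 | 0.979 |
| Continuity-corrected | 0.783 | 0.975 |
| Fisher's exact (by enumeration) | 0.796 | 0.977 |

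**Step 3: what the planned sample can detect.** Solving the same power formula for the difference above 23% at power 0.80 gives 9.9 points with 259/414 and 6.9 points with 518/828.

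**Step 4: precision.** The half-width of the 95% confidence interval for the difference is 1.960·SE1: 7.0 points with 259/414 and 5.0 points with 518/828.

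**Step 5: look for a reason for the factor of two.** 2 × 259 = 518, 2 × 414 = 828, and 518 + 828 = 1346. The factor is exactly the number of enrolment years, since patients are those "admitted to MTC critical care during the enrolment phase of the study (two years in total"). The sample size paragraph gives no allowance for non-consent, loss to follow-up, clustering by centre or regression covariates.

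**The case against.** The error runs in the safe direction. The primary comparison has more power than claimed, and no estimate, test or type I error rate is affected. The data come from routine care in an observational study, so extra patients face no study intervention, only consent and the 12-month contact. This is fair, and the point should not be read as a charge of underpowering or a call to recruit fewer patients.

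It is also true that 673 is enough only for one unadjusted comparison of two proportions. The protocol also plans multivariable regression, an examination of mode of death, and quality of life at one year among survivors who can be reached, at four centres. Those aims may well need more than 673, and a shortfall could weaken them even with the primary comparison secure. But the protocol does not offer any of them as the reason for doubling.

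Finally, the annual label may have begun as a recruitment rate that was merged with the power statement. The document cannot settle how it arose. The sentence nevertheless says that these numbers are needed each year in order to reject the null hypothesis at power 0.80, and as a statement about power that is wrong whatever its origin.

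**Conclusion.** The concern holds. Under the protocol's own rates, 673 patients in total meet the stated power of 0.80, and the planned 1346 give about 0.98. The stated power is therefore about 18 percentage points below that of the design, and the total is twice what the stated calculation supports. The conclusion assumes a two-sided alpha, the only sidedness that reproduces the figures, and a single pooled comparison of the two age groups, as the protocol describes. It concerns the unadjusted primary comparison only and does not show that 1346 is too many for the study's other aims.

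**What to change.** In the sample size paragraph of section 6:

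1. Remove the annual label and state that alpha is two-sided.
2. Say that 259 older and 414 younger patients, 673 in total, give 80% power for 33% against 23% in the primary comparison.
3. Say what 1346 delivers: about 98% power for that 10-point difference, or 80% power for about 7 points above 23%, with a 95% confidence interval of about ±5 points around the difference.
4. Give the actual reason for 1346. If it is kept for the regression models or the 12-month outcomes, say so and stop citing power 0.80 as its justification. That reason also guards against 673 being read as leave to stop at half the planned sample.

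The cost is a wording amendment. The total in the synopsis, the centre targets, recruitment and the analysis can all stay as they are.
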